## 4 STATISTICAL ANALYSES

### 4.1 GENERAL CONSIDERATIONS

In general, continuous data will be summarized using the number of observations available, mean, standard deviation (SDs), median, [Q1, Q3,] minimum, and maximum. Categorical and ordinal data will be summarized using the count and percentage of participants.

The baseline value is defined as the last available value before the first dose of investigational medicinal product (IMP). The MTD recommendation and DLT summary will be based on the DLT-evaluable population Cycle 1 data only excluding the 6 patients in the mini-expansion. All safety and efficacy analyses will be based on the safety population unless otherwise specified. The Part-1 and Part-2 analyses will be performed separately unless specified otherwise. Part-1 analyses will be presented by different dose levels, and Part-2 analyses will be presented by cohorts defined by different PD-L1 TPS. Part-3A analyses will be presented by dose levels, and Part-3B analyses, unless otherwise specified, will be presented overall. Part-4 analyses will be presented overall.

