- Concurrent increase in ALT and AST $>3 \times$ ULN AND total bilirubin $>2 \times$ ULN or INR >1.5 ULN in the absence of cholestasis and other causes (eg, viral hepatitis, other pre-existing or acute liver disease, or another drug capable of the observed injury), which may indicate severe drug-induced liver injury (possible Hy's law). Study drug should be withheld until AST, ALT, return to $<2 \times$ ULN and total bilirubin returns to $<1.5 \times$ ULN.
- Other project specific AESI(s)
 - QT (corrected or uncorrected) >480 msec or increased from baseline >60 msec (see [Section 7.1.1](#) QT prolongation management advice)
 - Thrombocytopenia Grade ≥ 3 or any grade if associated with clinically significant bleeding (see [Section 6.6.1.8](#) for hemorrhage management guidelines)

- Edema, including generalized/peripheral edema or facial/periorbital edema (see [Section 6.6.1.12](#) for edema management guidelines)
- All protocol defined potential or IMP related DLTs are considered as AESI, regardless of the cycle of occurrence (ie, after Cycle 1 in both escalation and expansion phases)

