9.4.3.1 Adverse events

The TEAE period is defined as the time from the first dose of study interventions up to 30 days after last dose of study interventions. Only TEAEs will be summarized in tables.

An overall summary of TEAEs will be provided. The number and percentage of participants who experience any of the following will be provided:

- TEAEs
- TEAEs of Grade ≥ 3
- Grade 5 TEAE (any TEAE with a fatal outcome during the treatment period)
- Serious TEAEs
- Serious treatment-related TEAEs
- TEAE leading to premature discontinuation of either SAR442720, pembrolizumab or adagrasib
- TEAE leading to definitive discontinuation
- TEAE leading to dose modifications
- Treatment-related TEAEs.
- Treatment-related TEAEs of Grade ≥ 3
- DLTs

The number and percentage of participants experiencing TEAEs by primary system organ class and PT will be summarized by NCI CTCAE version 5.0 grade (all grades and Grade ≥ 3). Similar tables will be prepared for treatment-related TEAEs, AESIs, TEAEs leading to treatment discontinuation, TEAEs leading to dose modification, delay, omission, serious TEAEs and TEAEs with fatal outcome.

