**Table 3 - Populations for analyses**

Population	Description
Enrolled	All participants who sign the ICF and have dose allocated to an intervention regardless of whether the intervention was received or not.
DLT-evaluable (only for Part-1 and Part-3A)	
Patients who take at least 4 of the 6 planned doses of SAR442720 (Part-1 and Part-3A) and 28 of the 42 planned doses of adagrasib (Part-3A) in the first cycle of the treatment and complete the DLT observation period.
 
OR
 
Patients who have any DLT observed in the DLT observation period.

PK	Patients who have at least one measurable SAR442720 concentration or at least one measurable pembrolizumab concentration after the first dose or at least one measurable adagrasib concentration after the first dose.
PD	Patients who have at least one PD marker result after the first dose
Safety	Patients who take at least one dose of any IMP (i.e., SAR442720, pembrolizumab, or adagrasib)
PK evaluable (Part-4 only)	Patients who complete all of cycle 1 and C2D1 with meal information, full PK, and no dose reduction/missed doses on C1D1, C1D15 and C2D1. Missing some PK samples may still be considered as evaluable and will be assessed case-by-cased.

Abbreviations: DLT = dose-limiting toxicity, ICF = informed consent form, PD = pharmacodynamic(s), PK = pharmacokinetic(s)

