### **Analysis of all adverse events**

An overall summary of TEAEs will be provided. The number and percentage of participants who experience any of the following will be provided:

- TEAEs
- Any grade  $\geq 3$  TEAE
- Any treatment emergent SAE
- Grade 5 TEAE (any TEAE with a fatal outcome during the treatment-emergent period or all-cause mortality)
- Serious TEAEs
- Serious treatment-related TEAEs.
- TEAE leading to premature discontinuation of either SAR442720 or pembrolizumab or adagrasib
- TEAE leading to permanent full intervention discontinuation (definitive discontinuation)
- TEAE leading to dose modifications
- Treatment-related TEAEs
- Treatment-related TEAEs of grade  $\geq 3$
- AESI
- DLTs

The AE summaries of participants experiencing TEAEs by primary SOC and preferred term will be generated with number (%) of participants experiencing at least one event in [Table 5](#). The analyses will be performed for all grades combined and for grades  $\geq 3$  according to NCI CTCAE v5.0. Similar tables will be prepared for treatment-related TEAEs, AESIs, TEAEs leading to treatment discontinuation, TEAEs leading to dose modification, delay, omission, serious TEAEs and TEAEs with fatal outcome.

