### **Analysis of adverse events of special interest (AESIs)**

Adverse events of special interest (AESIs) in Section 8.3.7 of protocol amendment 4 will be selected for analyses as indicated from CRF. Number (and percentage) of participants experiencing at least one event will be provided for each event of interest. Tables will be sorted as indicated in [Table 4](#).

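### SAP 4.1 leaves the six mini-expansion participants out of the Part-1 Cycle 1 DLT summary, so no single planned table reports the DLT rate in all DLT-evaluable participants

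*SAP*

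**What the plan says.** **The rule.** SAP 4.1 reads: "MTD recommendation and DLT summary will be based on the DLT-evaluable population Cycle 1 data only excluding the 6 patients in the mini-expansion". One exclusion therefore governs two things: the MTD recommendation and the descriptive DLT summary. Protocol 9.4.1 also limits the MTD recommendation to Cycle 1 data in the DLT-evaluable population. It contains no mini-expansion exclusion and sets no separate rule for a DLT summary. SAP 5.2 declares no change from the protocol.

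**Who the six are.** Protocol 9.2 and SAP 2 have them treated at the MTD, after it has been identified, to confirm it and settle the RP2D. The Protocol synopsis (number of participants) counts them within the 18 to 24 DLT-evaluable participants of Part-1. Neither Protocol Table 20 nor SAP Table 3 removes them from the DLT-evaluable population. One limb of the SAP definition takes in "Patients who have any DLT observed in the DLT observation period".

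**The endpoint.** SAP 1.2 lists Cycle 1 DLT incidence as a Part-1 primary endpoint.

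**Other planned displays that touch DLTs.**
- The TEAE overview in SAP 4.3 ("An overall summary of TEAEs will be provided. The number and percentage of participants who experience any of the following will be provided") ends its list with a DLTs row. Protocol 9.4.3.1 has the same row. Neither names a population for it. The SAP 4.1 default is "All safety and efficacy analyses will be based on the safety population unless otherwise specified", and SAP Table 3 defines that population as "Patients who take at least one dose of any IMP".
- The AESI table: "Number (and percentage) of participants experiencing at least one event will be provided for each event of interest". Protocol 8.3.6 adds: "All protocol defined potential or IMP related DLTs are considered as AESI, regardless of the cycle of occurrence".
- Disposition (SAP 4.2) gives the number in the DLT-evaluable population, without a DLT rate.

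**The concern.** The reason for excluding the six from the MTD recommendation is one of sequence: they enter after the MTD is identified, so they cannot feed its identification. That reason does not carry over to a descriptive summary of a primary endpoint. They are treated at that dose to test whether the MTD decision holds, and the DLT summary as written shows nothing of what happened to them.

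At stake is how Part-1 is read. The table labelled as the DLT summary would describe the escalation cohorts only, while another table could show a higher DLT count at the same dose, with nothing in the SAP to explain the difference. In addition, the term DLT summary is not defined. If it was meant to include the DLTs row of the TEAE overview, the six would drop out there too.

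**Working it through.** **Inputs**
- Escalation alone: 12 to 18 DLT-evaluable (Protocol 4.1.2).
- Mini-expansion: 6 (Protocol 9.2, SAP 2).
- Part-1 total: 18 to 24 DLT-evaluable (Protocol synopsis, Protocol 9.2, SAP 2).
- At the MTD: at least 6 treated before the mini-expansion; 3 to 6 assumed per dose level (Protocol synopsis).

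**Step 1. Reproduce the plan's total.** 12 + 6 = 18 and 18 + 6 = 24. The stated range is matched exactly, so the plan counts the six as DLT-evaluable.

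**Step 2. Share missing from the DLT summary.** Across Part-1, 6/24 = 25% to 6/18 = 33%. At the MTD, with the minimum of six from escalation and all six mini-expansion participants evaluable, 6/(6 + 6) = 50%.

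**Step 3. Can the all-evaluable rate be recovered from other output?**
- Numerator: Protocol 4.1.1 defines DLTs as first-cycle events, and anyone with a DLT in the observation period is DLT-evaluable by definition (SAP Table 3). A participant who is not evaluable therefore contributes no DLT. A count of DLTs in the safety population equals the count in all DLT-evaluable participants.
- Denominator: SAP 4.2 plans the DLT-evaluable count, and SAP 4.1 presents Part-1 by dose level.
- So (count in the DLTs row) / (DLT-evaluable count), both at the same dose, gives the rate. This works only if the DLTs row follows the safety-population default and not the SAP 4.1 exclusion.
- The percentage printed in that row is not the rate. On the default, its denominator includes participants who were not DLT-evaluable and who are replaced under Protocol 4.1.2.
- The AESI table does not help, because it mixes potential and IMP-related DLTs from any cycle.

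**Step 4. What the DLT summary alone can and cannot show.** The plan gives no confidence interval for DLTs. The 90% Clopper-Pearson level planned for ORR is borrowed here for illustration.

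| Data at the MTD | DLT summary under SAP 4.1 | All DLT-evaluable |
|---|---|---|
| No DLTs in either cohort | 0/6 = 0% (0 to 39.3%) | 0/12 = 0% (0 to 22.1%) |
| 0/6 in escalation, 2/6 in mini-expansion | 0/6 = 0% (0 to 39.3%) | 2/12 = 16.7% (3.0 to 43.8%) |

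In the second row, the DLTs row of the TEAE overview would show 2 at that dose if it follows the safety-population default.

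**Step 5. How likely is it that the two tables differ?** The target DLT rate is redacted, so true rates p are assumed. The chance of at least one DLT among the six is 1 - (1 - p)^6:
- p = 5%: 26.5%
- p = 10%: 46.9%
- p = 20%: 73.8%
- p = 30%: 88.2%

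**The case against.** The strongest reply is that nothing is lost. The numerator and denominator of the all-evaluable rate are both in planned output (Step 3), so what is missing is a printed rate in one place. A confirmation cohort that disagreed with escalation would show up as a higher count in the DLTs row. This largely stands. It depends, however, on reading the undefined DLT summary as not covering that row, and it asks the reader to divide figures from two tables to obtain a primary endpoint.

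A second reply is that the mini-expansion is a separate cohort. Protocol 4.2 describes it as a further look at safety, PK, PD and preliminary activity at the RP2D, so confining the DLT summary to the data behind the MTD decision could be deliberate. That would be a reasonable choice if stated with its reason. But Protocol 9.2 and SAP 2 give the cohort a confirmatory role at the MTD, and the plan counts its members as DLT-evaluable. The MTD and RP2D descriptions need to be reconciled.

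A third reply is that the entry missing from SAP 5.2 is bookkeeping, since the protocol's sequence already implies that the six cannot inform the MTD. That is fair as to substance; the entry is still owed.

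**Conclusion.** SAP 4.1 makes the summary of a Part-1 primary endpoint incomplete, in conflict with the plan's own sample-size count, both DLT-evaluable definitions and the stated purpose of the mini-expansion. It omits 25% to 33% of the DLT-evaluable participants in Part-1. The figure of one half at the MTD assumes exactly six from escalation and six evaluable in the mini-expansion.

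Three stronger readings are tempting, and the documents do not support them.
- A reader might infer that mini-expansion DLTs go unreported, or that the loss is the whole contrast of 0/6 against 0/12. That contrast describes the DLT summary only; on the safety-population default the rate can be rebuilt from SAP 4.3 and 4.2.
- A reader might infer that the dose choice is compromised. Protocol 4.1 bases the RP2D on all available data from all treated participants, and Protocol 4.3 records 200 mg BIW as already selected for the pembrolizumab combination.
- A reader might infer that the exclusion from the MTD recommendation is itself wrong. It follows from the order of events, and only the missing record in SAP 5.2 is at fault.

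The effect is on reporting. No formal test is planned, so no error rate or power is involved.

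**What to change.** 1. In SAP 4.1, limit the mini-expansion exclusion to the MTD recommendation.
2. Report Cycle 1 DLT incidence by dose level in all DLT-evaluable participants, with escalation, mini-expansion and pooled columns at the dose the mini-expansion received.
3. In SAP 4.3, state that the DLTs row of the TEAE overview includes the mini-expansion, and give its denominator.
4. In SAP 5.2, record the exclusion from the MTD recommendation, which Protocol 9.4.1 does not contain, with its reason.
5. Reconcile Protocol 4.2, which places the mini-expansion at the RP2D, with the Protocol synopsis, Protocol 9.2 and SAP 2, which place it at the MTD.

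The cost is wording and a few table columns. No new data are needed: Protocol 4.1.1 already requires each participant to be assessed for DLT at the end of Cycle 1 and the result to be entered on the eCRF.

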#### *Observation period*

The observation period will be divided into 3 segments:

- The **pre-treatment period** is defined as the period up to first IMP administration.
- The **on-treatment period** (ie, treatment-emergent [TE] period) is defined as the period from the first IMP administration to the last IMP administration + 30 days.
- The **post-treatment period** is defined as the period from the end of the on-treatment period. [After last IMP administration + 31 days]

### 4.2 PARTICIPANT DISPOSITIONS

The number (and percentage) of participants included in each of the analysis populations listed in [Table 3](#) will be summarized.

Screen failures are defined as participants who consent to participate in the study but are not subsequently dosed. The number (and percentage) of screen failures and reasons for screen failures will be provided.

Regarding intervention discontinuation, the following definitions will be used:

- Permanent **full** intervention discontinuation is defined as the discontinuation of all the study drugs

The number (and percentage) of participants in the following categories will be provided:

- Enrolled population
- Safety population

- DLT evaluable population (only for Part-1 and Part-3A)
- Pharmacokinetics population
- Pharmacodynamic population
- Participants who did not complete the study treatment as per protocol and main reason for full treatment discontinuation and treatment withdrawal by subject
- Participants who did not complete study/follow-up period as per protocol and main reason for study discontinuation
- Subject survival status

#### Protocol deviations

Critical and major protocol deviations (automatic or manual) will be summarized in the safety population.

### **4.3 SAFETY ENDPOINT(S)**

Safety endpoints including incidence and severity of AEs and SAEs and laboratory abnormalities are the primary endpoints for Part-1 and Part-3A and secondary endpoints for Part-2, Part-3B, and Part-4.

All AEs will be graded according to National Cancer Institute Common Terminology for Adverse Events (NCI-CTCAE) version 5.0 and coded to a lower-level term (LLT), preferred term (PT), high-level term (HLT), high-level group term (HLGT), and associated primary system organ class (SOC) using the Medical Dictionary for Regulatory Activities (MedDRA) version 24.1.

The AEs will be analyzed in the following 3 categories:

- Pre-treatment AEs: AEs that developed, worsened or became serious during the pre-treatment period
- Treatment-emergent adverse events (TEAE)s: AEs that developed, worsened or became serious during the on-treatment period
- Post-treatment AEs: AEs that developed, worsened or became serious during the post-treatment period

Similarly, the deaths will be analyzed in the on-treatment and post-treatment periods. The primary focus of AE reporting will be on TEAEs. Pre-treatment and post-treatment AEs will be described separately.

An AE with incomplete or missing date/time of onset (occurrence, worsening, or becoming serious) will be classified as a TEAE unless there is definitive information to determine it is a pre-treatment or a post-treatment AE.

If the assessment of the relationship to IMP is missing for an AE, this AE will be assumed as related to IMP. If the severity/grade is missing for one of the treatment-emergent occurrences of an AE, the severity/grade will be imputed with the maximal severity of the other occurrences. If the severity is missing for all the occurrences, the severity/grade will be left as missing.

Multiple occurrences of the same event in the same participant will be counted only once in the tables within a treatment phase, using the maximum (worst) grade by treatment phase. Summaries will be provided for all grades combined and for grade  $\geq 3$  (including Grade 5). Missing grades, if any, will be included in the “all grades” category.

The AE tables will be sorted as indicated in [Table 4](#).

**Table 4 - Sorting of AE tables**

AE presentation	Sorting rules
SOC and PT	By the internationally agreed SOC order and decreasing frequency of PTs a
PT	By decreasing frequency of PTs a

a Sorting will be based on the overall incidence

### **Analysis of all adverse events**

An overall summary of TEAEs will be provided. The number and percentage of participants who experience any of the following will be provided:

- TEAEs
- Any grade  $\geq 3$  TEAE
- Any treatment emergent SAE
- Grade 5 TEAE (any TEAE with a fatal outcome during the treatment-emergent period or all-cause mortality)
- Serious TEAEs
- Serious treatment-related TEAEs.
- TEAE leading to premature discontinuation of either SAR442720 or pembrolizumab or adagrasib
- TEAE leading to permanent full intervention discontinuation (definitive discontinuation)
- TEAE leading to dose modifications
- Treatment-related TEAEs
- Treatment-related TEAEs of grade  $\geq 3$
- AESI
- DLTs

The AE summaries of participants experiencing TEAEs by primary SOC and preferred term will be generated with number (%) of participants experiencing at least one event in [Table 5](#). The analyses will be performed for all grades combined and for grades  $\geq 3$  according to NCI CTCAE v5.0. Similar tables will be prepared for treatment-related TEAEs, AESIs, TEAEs leading to treatment discontinuation, TEAEs leading to dose modification, delay, omission, serious TEAEs and TEAEs with fatal outcome.

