- The disease/disorder being studied or expected progression, signs, or symptoms of the disease/disorder being studied, unless more severe than expected for the participant’s condition.
- Medical or surgical procedure (eg, endoscopy, appendectomy): the condition that leads to the procedure is the AE.
- Situations in which an untoward medical occurrence did not occur (social and/or convenience admission to a hospital).
- Anticipated day-to-day fluctuations of pre-existing disease(s) or condition(s) present or detected at the start of the study that do not worsen.

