10.3.2 Definition of SAE

If an event is not an AE per definition above, then it cannot be an SAE even if serious conditions are met (eg, hospitalization for signs/symptoms of the disease under study, death due to progression of disease).

A SAE is defined as any untoward medical occurrence that, at any dose:

- Results in death**
- Is life-threatening**

The term “life-threatening” in the definition of “serious” refers to an event in which the participant was at risk of death at the time of the event. It does not refer to an event, which hypothetically might have caused death, if it were more severe.

c) Requires inpatient hospitalization or prolongation of existing hospitalization

In general, hospitalization signifies that the participant has been detained (usually involving at least an overnight stay) at the hospital or emergency ward for observation and/or treatment that would not have been appropriate in the physician's office or outpatient setting. Complications that occur during hospitalization are AEs. If a complication prolongs hospitalization or fulfills any other serious criteria, the event is serious. When in doubt as to whether "hospitalization" occurred or was necessary, the AE should be considered serious.

Hospitalization for elective treatment of a pre-existing condition that did not worsen from baseline is not considered an AE.

d) Results in persistent disability/incapacity

- The term disability means a substantial disruption of a person's ability to conduct normal life functions.
- This definition is not intended to include experiences of relatively minor medical significance such as uncomplicated headache, nausea, vomiting, diarrhea, influenza, and accidental trauma (eg, sprained ankle) which may interfere with or prevent everyday life functions but do not constitute a substantial disruption.

e) Is a congenital anomaly/birth defect

f) Other situations:

- Medical or scientific judgment should be exercised in deciding whether SAE reporting is appropriate in other situations such as important medical events that may not be immediately life-threatening or result in death or hospitalization but may jeopardize the participant or may require medical or surgical intervention to prevent one of the other outcomes listed in the above definition. These events should usually be considered serious.

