### **Analysis of deaths**

The deaths will be summarized by observation period ie, number (%) of deaths during the on-treatment period and number (%) of deaths during post-treatment period.

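### The SAP's Grade 5 TEAE row adds all-cause mortality, so deaths that are not adverse events would be counted as fatal TEAEs

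*SAP*

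**What the plan says.** SAP 4.3, under its analysis of all adverse events, lists the rows of an overall TEAE summary. One of them is "Grade 5 TEAE (any TEAE with a fatal outcome during the treatment-emergent period or all-cause mortality". Protocol 9.4.3.1 gives the same row as "Grade 5 TEAE (any TEAE with a fatal outcome during the treatment period" and adds: "Only TEAEs will be summarized in tables".

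The surrounding definitions are these:

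- **TEAE (SAP 4.3):** "AEs that developed, worsened or became serious during the on-treatment period".
- **On-treatment period (SAP 4.1):** it "is defined as the period from the first IMP administration to the last IMP administration + 30 days".
- **Not an AE (protocol 10.3.1):** "The disease/disorder being studied or expected progression, signs, or symptoms of the disease/disorder being studied, unless more severe than expected".
- **Not an SAE (protocol 10.3.2):** an event outside the AE definition cannot be an SAE, and the examples given are "hospitalization for signs/symptoms of the disease under study, death due to progression of disease".
- **Deaths (SAP, Analysis of deaths):** "The deaths will be summarized by observation period", with separate counts for the on-treatment and post-treatment periods.

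SAP Table 5 separately plans a table of TEAEs leading to death by system organ class and preferred term, with no all-cause limb. SAP Appendix 2, which is the place to record departures from the protocol's analyses, is marked not applicable.

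**The concern.** A Grade 5 TEAE is an adverse event that starts, worsens or becomes serious on treatment and ends in death. All-cause mortality is a different quantity, with no requirement that an adverse event was involved. Joining the two with *or* makes the row a count of deaths under the label of fatal TEAEs.

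SAP 4.3 names the incidence and severity of AEs as primary endpoints for Part-1 and Part-3A. The trial is uncontrolled, so no comparator arm would show a reader that a high figure in this row came from the underlying cancer. The change also departs from the protocol without being declared.

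**Working it through.** The plan attaches no figure to this row, so there is nothing to reproduce. The check is a comparison of definitions.

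**Step 1. Who enters the row.** Divide participants in a group of size N who die into three exclusive sets:

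- *a*: a TEAE had a fatal outcome within the treatment-emergent period.
- *b*: death fell within that period but was not the outcome of an AE, for example expected progression under protocol 10.3.1 and 10.3.2.
- *c*: death came after last IMP + 30 days.

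| Definition | Row |
|---|---|
| Protocol 9.4.3.1 | a / N |
| SAP 4.3, all-cause limb confined to the treatment-emergent period | (a + b) / N |
| SAP 4.3, literal wording (the period qualifies only the first limb) | (a + b + c) / N |

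Since b and c cannot be negative, the SAP row is never below the protocol row. It is above it as soon as one death in set *b* occurs, on either reading.

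**Step 2. Whether set *c* is observed.** Protocol 7.1.1 sends participants who do not withdraw consent into follow-up until death, end of study or loss to follow-up. The schedules for Part-1, Part-2 and Part-4 include telephone contact for survival. The synopsis says follow-up does not apply to Part-3, and the Part-3 schedule has no follow-up column. Post-treatment deaths would therefore arise mainly in Parts 1, 2 and 4.

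**Step 3. Consistency with other SAP output.**

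- Table 5 counts TEAEs leading to death, so sets *b* and *c* are absent from it. The overview row and Table 5 could give different counts.
- SAP 4.3 includes Grade 5 in Grade 3 or higher. A participant in set *b* or *c* with no TEAE of Grade 3 or higher would be in the Grade 5 row but not in the Grade 3 or higher row, so the subset would not nest in its parent.
- All of *a*, *b* and *c* already appear in the analysis of deaths, split by period. The extra limb adds no information.

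**Step 4. Arithmetic with assumed counts only.** Take one Part-2 cohort, N = 20, with a = 1, b = 2 and c = 5. These three counts are invented to separate the readings.

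- Protocol: 1/20 = 5%.
- SAP, narrow reading: (1 + 2)/20 = 15%.
- SAP, literal reading: (1 + 2 + 5)/20 = 40%.

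**The case against.** The strongest reply is that the row sits under a Grade 5 TEAE label, in a list introduced as a summary of TEAEs, and that the SAP bounds TEAEs by the on-treatment period. A programmer could reasonably confine the all-cause limb to that period. This stands as far as it goes. A reader might infer that post-treatment deaths will certainly be counted, and the documents do not support that: it follows from the literal wording but is not the only reading. The narrower reading does not rescue the row, however, because set *b* still enters.

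Second, the boundary between progression and adverse event is not absolute. Protocol 10.3.1 excludes expected progression unless it is more severe than expected, and two of its bullets on lack of efficacy point in different directions. Some progression-related deaths may properly be Grade 5 AEs. That shrinks set *b* without emptying it.

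Third, nothing is decided on this row. Protocol 9.1 states no formal hypothesis, and SAP 4.7 calls the safety analysis essentially descriptive. The MTD recommendation uses Cycle 1 data in the DLT-evaluable population (SAP 4.1), and the RP2D draws on all available safety, PK, pharmacodynamic and efficacy data (protocol 4.1). Correct counts of fatal TEAEs and of deaths by period are planned elsewhere, so a discrepancy would be visible to a careful reader. All of this stands, and it limits the severity.

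**Conclusion.** The SAP's definition is wrong as written. It contradicts the protocol's version of the row and the SAP's own meaning of a TEAE, and the departure is not declared. Inclusion of on-treatment deaths that are not AEs does not depend on how the phrase is read. Inclusion of deaths after last IMP + 30 days depends on the literal reading. The direction is certain: the row can only be inflated.

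A reader might want to state a multiple for the overstatement. The documents give no fatal-TEAE rate and no death proportion for any part, so any multiple would be a ratio of two assumed numbers. A reader might also say that the row measures survival. It does not: it is a count of participants with no time-to-event content. Nor do the documents support treating this as a threat to dose selection or to the trial's conclusions. The effect is confined to one descriptive overview row, with correctly defined counts elsewhere, which makes it a should-fix.

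**What to change.** In SAP 4.3, delete *or all-cause mortality* from the Grade 5 TEAE row. This restores the protocol's definition and removes this source of disagreement with Table 5 and with the Grade 3 or higher row. Report all-cause deaths only under the SAP's analysis of deaths.

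If the sponsor wants an all-cause count beside the TEAE overview, give it a separate row, labelled as deaths, with a stated time window, and record the addition in SAP Appendix 2.

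The cost is one phrase and the matching table shell, to be settled before database lock. No data collection, sample size or other analysis changes.
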